### **Non-sensor based secondary clinical**

1. Daily average total insulin dose
2. Daily average basal insulin dose
3. Daily average bolus dose
4. Average number of boluses of rapid acting insulin per day

### **Non-sensor based secondary patient-reported (psychosocial)**

1. T1-DDS: mean-item score
2. EQ-5D-5L (This outcome will not be covered in the SAP but instead will be included in the Health Economics Analysis Plan.)
3. PHQ-9 total score
4. D-FISQ total score
5. DEPS-R total score

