7.2 Inclusion Criteria

1. The participant is ≥ 16 years old
2. The participant has type 1 diabetes, as defined by WHO for at least 1 year or is confirmed C-peptide negative if duration of diabetes is < 1 years
3. Participant is treated with insulin pump or multiple daily injection for at least 12 weeks and no plans to change treatment modality during next 28 weeks
4. The participant is literate in English for safe study conduct
5. Screening HbA1c $\geq 7.5\%$ (58.5mmol/mol) and $\leq 11\%$ (97 mmol/mol) based on analysis from local, central or third party external laboratory

6. The participant is willing to wear study glucose sensor and scan for glucose levels at frequent intervals
7. The participant is willing to follow study specific instructions to improve glucose control
8. Female participants of child bearing age should be on effective contraception or not sexually active/no plans for pregnancy in the next 8 months.
9. The participant adopting a virtual pathway through the trial is able and willing to post study devices, questionnaires and blood collection kits back to the research team or to the laboratory using pre-paid postal services
10. The participant adopting a virtual pathway through the trial has internet connection, appropriate videoconferencing software and supporting devices to undertake video consultations where necessary.

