8.2 Intended Purpose

The intended purpose of the investigational treatment is flash-glucose monitoring intended at replacing finger-stick glucose levels.

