13.3 Insulin pumps

Participants already on insulin pump therapy will continue their usual insulin pump throughout the study.

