26.5 Appendix 5: Diabetes fear of injecting and self-testing (D-FISQ) questionnaire

SELF-INJECTING OF INSULIN

		(almost) never	sometimes	often	(almost) always
When I have to inject myself:					
1.	I become restless	0	0	0	0
2.	I feel tense	0	0	0	0
3.	I feel afraid	0	0	0	0
4.	I worry about it	0	0	0	0
5.	I feel nervous	0	0	0	0
6.	I brood about it	0	0	0	0

SELF-TESTING OF BLOOD GLUCOSE

		(almost) never	sometimes	often	(almost) always
When I have to prick my finger:					
7.	I become restless	0	0	0	0
8.	I try to avoid it	0	0	0	0
9.	I feel tense	0	0	0	0
10.	I feel afraid	0	0	0	0
11.	I worry about it	0	0	0	0
12.	I feel nervous	0	0	0	0
13.	I brood about it	0	0	0	0
14.	I try to postpone it	0	0	0	0
15.	I get angry	0	0	0	0

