### 1.2.2 Study Objectives

The primary objective is to assess the clinical efficacy of flash glucose monitoring with FSL2 device relative to that with self-monitoring of blood glucose on glycated haemoglobin A1c (HbA1c).

Secondary clinical and psychosocial objectives are, respectively:

- to assess the clinical efficacy of flash glucose monitoring with FSL2 device relative to that with self-monitoring of blood glucose on sensor-based glucose metrics (e.g. time spent in target glucose range 3.9 to 10 mmol/L).
- to evaluate the participants' responses in terms of quality of life, diabetes related distress, diabetes treatment satisfaction, low mood, needle burden and disordered eating behaviours using validated questionnaires.

The safety objective is to evaluate time spent in hypoglycaemia (sensor glucose levels < 3.0 mmol/l and other sensor based biochemical hypoglycaemia) and number of episodes of severe hypoglycaemia with FSL2 and self-monitoring of blood glucose.

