### 5.3 Missing data

Should we have more than 10% missing HbA1c at 24 weeks (or more than a 10% difference between missing data percentages in the two arms), multiple imputation will be used in order to implement a more complete ITT analysis of the substantive ANCOVA model. The imputation model will include baseline and 12-week HbA1c, all the baseline variables used in the outcome model and any other recorded variables found to be predictive of missing the 24-week outcome in exploratory analyses (via a logistic regression model, with terms included using a 10% significance level). A minimum of 50 imputations will be performed, although this will be increased if the percentage of missing data is greater than expected. We will perform multiple imputation by chained equations (MICE).

Complete cases analyses will be implemented for all secondary outcomes. Should we have up to 30% missing items for any subscale (or overall questionnaire if no subscales), the missing item will be imputed by the mean response of the rest items completed within participant for that particular subscale. If more than 30% missing items the response to this subscale will be set to missing, as will be the overall response of the questionnaire.

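### The only D-FISQ outcome is the 15-item total, which can dilute an effect on the finger-prick items and is lost when a pump user leaves the injection items blank

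*SAP*

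**What the plan says.** Needle burden is one of the psychosocial objectives. SAP 1.2.2 lists it among "low mood, needle burden and disordered eating behaviours using validated questionnaires". The outcome that serves it, in SAP 5.1.2, is the "D-FISQ total score". SAP 5.2.2 analyses it by ANCOVA, adjusted for its own baseline and the minimisation variables. No part score is listed.

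Protocol Appendix 5 prints the form in two headed parts. Items 1-6 follow the stem "When I have to inject myself" and items 7-15 follow "When I have to prick my finger". The four response options run from (almost) never to (almost) always. There is no not-applicable option, no instruction for pump users and no scoring key.

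Protocol 8.2 describes the device as "flash-glucose monitoring intended at replacing finger-stick glucose levels". Pump users are eligible: Protocol 7.2 requires that the "Participant is treated with insulin pump or multiple daily injection for at least 12 weeks". They also stay on the pump; under Protocol 13.3, "Participants already on insulin pump therapy will continue their usual insulin pump throughout the study".

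SAP 5.3 sets the missing-item rule. It begins "Should we have up to 30% missing items for any subscale (or overall questionnaire if no subscales" and fills such gaps with the participant's mean on the completed items. Above 30%, both the subscale and the overall questionnaire score are set to missing. Secondary outcomes are analysed as complete cases.

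**The concern.** Nine of the fifteen items concern what the intervention replaces, and six concern insulin injection. Adding the six brings in variation that the device does not directly target, so a real fall in fear of finger-pricking is harder to see in the total.

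The second problem comes from the SAP's own missing-item rule. A pump user may reasonably leave the injection block blank. The rule then discards the whole score, including nine complete answers about finger-pricking. Because the ANCOVA uses baseline, a blank block at either screening or week 24 is enough to drop that person. A pump user who ticks the lowest category instead keeps a score, but six of its items say little about that person's treatment. The SAP covers neither case.

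At stake are the sensitivity of the needle-burden result and whether it describes pump users as well as injection users.

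**Working it through.** **Reference sample size.** The documents give no effect size or power for the D-FISQ, so the primary-outcome sample serves only as a reference. SAP 2.3 assumes a difference of 0.4% and an SD of 0.8%, a standardised effect of 0.5. At 64 per arm and two-sided 5%, a two-sample t-test has power 0.801. This reproduces the stated 80%.

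**Missing-item rule.** Six blank injection items are 6/15 = 40% of the questionnaire, or 6/6 = 100% of the injection part if that part is treated as a subscale. Both exceed 30%. The most that may be blank is 4 of 15 (0.30 × 15 = 4.5) or 1 of 6 (0.30 × 6 = 1.8). The total is therefore missing on either reading. Scored alone, the finger-prick part of the same participant has 0 of 9 items missing and would be kept.

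**Dilution.** Assumptions, none of them in the documents:
- each item has unit variance;
- the correlation within a part is w = 0.5 to 0.7;
- the correlation between parts is b = 0.2 to 0.6, and no greater than w;
- the effect falls on items 7-15 only.

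Then:
- Var(finger-prick part) = 9 + 72w
- Var(injection part) = 6 + 30w
- Cov(parts) = 54b
- Ratio of standardised effects, total to finger-prick part = sqrt[Var(finger-prick) / (Var(finger-prick) + Var(injection) + 2 Cov)]

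| w | b | Var finger-prick | Var injection | 2 Cov | Var total | Ratio |
|---|---|---|---|---|---|---|
| 0.7 | 0.2 | 59.4 | 27.0 | 21.6 | 108.0 | 0.74 |
| 0.6 | 0.4 | 52.2 | 24.0 | 43.2 | 119.4 | 0.66 |
| 0.5 | 0.5 | 45.0 | 21.0 | 54.0 | 120.0 | 0.61 |
| 0.6 | 0.6 | 52.2 | 24.0 | 64.8 | 141.0 | 0.61 |

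The condition b ≤ w is needed. At w = 0.5 and b = 0.6 the implied correlation between the two part scores is 32.4/sqrt(45 × 21) = 1.05, which is impossible.

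For illustration, an effect of 0.5 SD on items 7-15 has power 0.80 at 64 per arm. On the total it becomes 0.30 to 0.37 SD, with power about 0.40 to 0.55 (unadjusted t-test).

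**Effect of baseline adjustment.** Take w = 0.6, b = 0.4 and a baseline-to-follow-up correlation of 0.5 for the finger-prick part. Suppose the injection part is more stable, at 0.7 to 0.85, and the cross-part correlations over time shrink by the geometric mean of the two. The ratio then rises from 0.66 to 0.70-0.73. If both parts are equally stable (0.5), it stays at 0.66.

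**Number of pump users lost.** This cannot be computed. The documents give neither this trial's pump share nor a rate of blank injection blocks. The one-third figure in Protocol 4.3 describes another trial, in well-controlled type 1 diabetes.

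**The case against.** A reader might infer that flash monitoring cannot change the injection items. The documents do not support that. Protocol Appendix 9 has insulin dosing reviewed in both arms and encourages participants to alter therapy from their data, and boluses per day is itself a secondary outcome. Injecting could change, and for injection users more boluses would mean more injections. This also supports keeping the total: the objective is needle burden, not fear of finger-sticks alone, and the total would capture a net effect. In an open-label trial, replacing it with only the items expected to favour the device would be a debatable trade. Both arguments stand, but they are reasons to keep the total, not to omit a part score.

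A reader might also infer that losing pump users biases the comparison. Treatment modality is a minimisation factor and a covariate, so the loss should be roughly equal in the two arms. Nor is it established that pump users skip the block, since they can tick (almost) never.

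Items 7-15 have their own weakness. Flash users may rarely prick their finger: Protocol 4.3 reports 0.5 tests a day among users in an earlier trial. Blanks could then fall mainly in one arm. The total shares this problem, but it needs watching. Against it, Appendix 9 tells flash users to do a blood test when the device suggests a hypo, so the items still apply to them.

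Finally, finger-stick frequency and the GMSS Behavioral Burden subscale are already compared between arms. They cover burden of monitoring, but not fear. The fact that GMSS has planned subscales is weak evidence of an oversight here, because Appendix 2 prints GMSS subscale scoring and Appendix 5 prints none.

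**Conclusion.** The point holds as a cheap improvement to a secondary outcome. Two things follow directly from the documents: the only D-FISQ outcome mixes nine targeted items with six that are not directly targeted, and a blank injection block removes the whole score under SAP 5.3 (40% or 100% against a 30% limit) even when all finger-prick items are complete.

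The size of the dilution, a standardised effect of roughly 0.61 to 0.74 of that on items 7-15, is conditional. It requires that the injection items change little and that the assumed item variances and correlations hold, and it is before baseline adjustment, which may bring the ratio closer to 1. The number of pump users without a score is unknown; the cost is precision and a result that leans towards injection users. Bias between arms is not shown, and neither the primary analysis nor its sample size is affected.

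**What to change.** - **SAP 5.1.2 and 5.2.2:** add the D-FISQ self-testing score (items 7-15) as a needle-burden outcome for all participants, with the same ANCOVA adjusted for its own baseline. Keep the 15-item total.
- **SAP 5.3:** apply the 30% rule to the self-testing part on its own, so that blank injection items do not remove it. State how items 1-6 and the total are scored for CSII users.
- **Reporting:** give missingness of items 7-15 by arm.

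The cost is SAP wording, since every item is already collected, and one more secondary comparison in a plan that makes no multiplicity adjustment (SAP 3.1).

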### **Harms outcomes**

1. Frequency of severe hypoglycaemic episodes as defined by American Diabetes Association. For purposes of analysis, a severe hypoglycaemic event will be defined as an event requiring assistance of another person actively to administer carbohydrate, glucagon, or other resuscitative actions. These episodes may be associated with sufficient neuroglycopenia to induce seizure or coma. If plasma glucose measurements are not available during such an event, neurological recovery attributable to the restoration of plasma glucose to normal is considered sufficient evidence that the event was induced by a low plasma glucose concentration.
2. Frequency of significant ketosis events (plasma ketones  $>3\text{mmol/l}$ )
3. Nature and severity of other adverse events including the following categories:
  - *Hospital admissions*
  - *Skin reactions*

#### ***5.1.3 Process evaluation (utility and acceptability) outcomes***

1. FLS2 device utilization data (FLS2 trial arm only), including:
  - a. average number of scans per day (7:00-23:00 hours);
  - b. average number of scans per night (23:00-7:00 hours);
  - c. average number of scans over the full 24-hour period;
  - d. average number of days of usage per week.

2. Average number of finger-stick glucose level tests per calendar day (as collected at visits 1, 4, 5, and 7: average over the last 14 days).
3. DTSQ total score
4. GMSS (and subscales) mean-item score

## 5.2 Analysis methods

All 12-week and 24-week outcome data will be presented descriptively, both overall and within treatment group, using mean (SD), median (IQR) or frequency (percentage), as appropriate. Mean (SD) change of HbA1c will also be presented overall and by treatment group. All statistical tests will use a 2-sided significance level of 5% (unless otherwise specified), and all confidence intervals will be presented at a level of 95% and will be two sided.

### 5.2.1 Primary outcome analysis

The primary outcome analysis will evaluate between group differences in HbA1c levels at the end of the 24-week treatment period. An ANCOVA model will be used, with 24-week HbA1c as the outcome and trial arm effect as the focus, with adjustment for baseline HbA1c and the other baseline variables included in the minimisation allocation algorithm (study centre, treatment modality, prior participation in structured education course and current use of bolus calculator) as covariates.

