9.4 Visit 3: Adherence assessment, randomisation and start of study treatment

During Visit 3, participant's adherence / tolerance of using the flash-CGM over preceding 14 days will be assessed. To proceed with the study participant should have worn the blinded glucose monitoring device for at least 10 days' during last 14 days of run-in period. If the participant fails to demonstrate adherence or develops any significant allergy or intolerance to the glucose sensor, the study will be terminated and participant will be removed from the study. If the sensor records less than 10 days' worth of data due to a problem with the sensor itself (premature sensor failure) rather than a participant related issue, a new sensor should be inserted to get a minimum of total 10 days' worth of data. In cases in which there is a premature sensor failure, participant randomisation should only proceed once a minimum total of 10 days data has been downloaded. Participants who are opting for virtual consultations and who have <10 days data, will be provided with a new FSL2 pro sensor and reader to obtain the minimum data requirements prior to randomisation.

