12.1.2 Subcutaneous Glucose Monitoring

At least 10 days of blinded continuous glucose (Freestyle Libre Pro) data will be collected prior to the randomisation with the aim of gaining knowledge of the specific participant's glucose control characteristics at screening and assessing adherence before the beginning of any intervention arm. Participants in the intervention arm will be encouraged to upload freestyle libre 2 data at regular intervals.

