14.1 Sample size

The sample size calculation (128 evaluable cases from 150 randomised 1:1, up to 180 recruited to allow for any dropouts pre-randomisation) was premised on a between trial arm t-test for follow-up HbA1c values (2-tail alpha = 0.05, power = 0.80 when the true mean difference is 0.4% and the SD is 0.8% i.e. Standardised Effect Size [SES] = 0.5). There is expected to be a moderate-to-large correlation between baseline and follow-up HbA1c values, so the planned use of ANCOVA (see 14.2 and 14.3) will in fact have greater power (assuming other inputs unchanged).

We chose delta (MCID) of 0.4% as this is consistent with other relevant trials (REPOSE (31) used 0.5%, DIAMOND (10) used 0.4% and GOLD (11) used 0.3%, for delta at the design stage), although there is no consensus as to which of these values is most appropriate. We also considered findings from other RCTs (DIAMOND (10) 0.6%, GOLD (11) 0.43%, as detailed in our application) and a recent meta-analysis of trials and longitudinal observational studies (32) which have suggested that an effect of the order of 0.43%-0.7% might be expected, somewhat greater than the potential range for delta of 0.3%-0.5%, and therefore chose to power the proposed trial on a delta of 0.4%, deeming

that this was the most efficient approach without potentially over-powering the trial (an interim analysis is not possible given the length of follow-up relative to the recruitment period).

The assumed SD was informed by published results from the DIAMOND (10) and GOLD (11) trials, although the eligible baseline HbA1c values for these trials were 7.5 to 10.0% and $\geq 7.5\%$, respectively, which each differ somewhat from the 7.5% to 11.0% range intended for this trial (it is likely that the SD will be lower with a narrower eligibility range, suggesting that our SD may lie between the 0.8 reported for DIAMOND (10) and the 0.9 implied for GOLD (11)). Increasing SD and baseline/follow-up correlation (ρ) act in opposite directions on power for a given sample size – the table below illustrates reasonable power for a range of plausible values.

Power for an ANCOVA with 128 evaluable cases (150 randomised 1:1):

		rho			
SES = delta/SD		0	0.3	0.5	0.7
0.44 (e.g. 0.4/0.9)		0.70	0.73	0.81	0.93
0.50 (e.g. 0.4/0.8)		0.80	0.84	0.90	0.98

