As can be seen in the table above, if the correlation (ρ) between baseline and 6-month HbA1c values is at least 0.5 (consistent with a scatterplot provided in the DIAMOND (10) paper), power will be at least 90% for a SES of 0.5, but will still detect a SES of 0.44 (e.g. SD 0.9 rather than 0.8) with at least 81% power. We therefore believe that our choice of 128 participants with evaluable HbA1c at the 6-month time-point is optimal.

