## 2.3 Sample size

Assuming a standard deviation of 0.8% and treatment difference of 0.4% - 128 participants (64 per each arm) with primary outcome will give 80% power to detect the difference between treatment groups at 2-sided type 1 error = 5%. Recruitment target is 180 participants (25 to 30 per centre) aiming for 150 to be randomised following the adherence run-in period, and allowing for 15% post-randomisation attrition.

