#### **5.2.3 Sensitivity analyses**

Sensitivity analyses will examine robustness of the primary outcome results to assumptions regarding missing data by performing multiple imputation (see Section 5.3).

The primary outcome analysis will also be repeated having included additional covariates for the consideration of improved precision. These covariates will include age, sex, BMI duration of diabetes, deprivation index quintile.

Complier-Adjusted Causal Effect (CACE) will be used, implemented using an instrumental variables approach, to estimate the causal effect of the FSL device glucose monitoring relative to finger-stick glucose monitoring. Appropriate definitions of non-compliance (adherence) will be investigated within this sensitivity analysis, including the simple definition in the finger-stick monitoring arm of non-compliance equating to use of FSL device glucose monitoring for at least 10 days between the 3-month and 6-month outcome assessment.

Additional sensitivity analyses will be conducted to assess the impact of primary outcome data collected outside the visit window as specified in the protocol, that is:

- +/- 2 weeks of the planned visit date or
- +/- 4 weeks of the planned visit date.

Further sensitivity analyses will be performed to assess the potential impact of COVID-19 on the primary outcome. These will include the exclusion of participants whose treatment or outcome assessment was deemed severely impacted by COVID-19.

Finally, additional sensitivity analyses will be introduced to examine for the impact of protocol deviations or other unexpected events that may not have been captured in the protocol, including the impact on key secondary outcomes, where deemed necessary.

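### The primary HbA1c model, and the SAP's own precision model, leave out run-in mean sensor glucose: a valid analysis that misses an efficiency gain of nil to modest size

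*SAP*

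**What the plan says.** **Primary model.** SAP 5.2.1 fits an ANCOVA to 24-week HbA1c "with adjustment for baseline HbA1c and the other baseline variables included in the minimisation allocation algorithm", which it lists as centre, treatment modality, structured education and bolus calculator use. Protocol 14.2.1 agrees.

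**Precision model.** SAP 5.2.3 repeats the primary analysis with further covariates, giving precision as the reason: "These covariates will include age, sex, BMI duration of diabetes, deprivation index quintile". None of these measures glycaemia.

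**Run-in sensor data.** Protocol 9.4 makes wearing the blinded sensor for at least 10 of the last 14 run-in days a condition of going on to randomisation. After premature sensor failure, "participant randomisation should only proceed once a minimum total of 10 days data has been downloaded". Protocol 12.1.2 says at least 10 days of data are collected before randomisation, "with the aim of gaining knowledge of the specific participant's glucose control characteristics at screening".

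**Existing use of those data.** SAP 5.1.2 already defines average glucose as a sensor metric. SAP 5.2.2 adjusts the sensor outcomes for run-in sensor values and baseline HbA1c together. The HbA1c outcomes get no such term.

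**The concern.** Baseline HbA1c is a single screening value, scheduled 2 to 3 weeks before randomisation, and the same value decides eligibility within 7.5% to 11%. Run-in mean glucose is a second, later measure of the same underlying quantity and is not used for selection. A covariate earns its place in an ANCOVA by predicting the outcome beyond what the model already holds. On that ground run-in glucose is a more natural candidate than BMI or deprivation, which the precision model does include. If it carries independent information, leaving it out makes the confidence interval for the primary effect wider than it need be, with data already in hand.

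The imputation model is affected too. The design expects 22 of 150 randomised participants to lack the outcome (150 − 128 = 22; 22/150 = 14.7%). That exceeds the 10% trigger in SAP 3.3 and 5.3, so if attrition runs as planned, multiple imputation becomes the primary analysis. Beyond the HbA1c values and the outcome-model covariates, SAP 5.3 admits only variables that predict missingness. A variable that predicts the outcome but not missingness would be left out.

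**Working it through.** **Inputs from the documents**
- Design: "2-tail alpha = 0.05, power = 0.80 when the true mean difference is 0.4% and the SD is 0.8" per cent (Protocol 14.1), a standardised effect size (SES) of 0.5.
- Numbers: "128 evaluable cases from 150 randomised 1:1" (Protocol 14.1), so 64 per arm; SAP 2.3 describes this as "allowing for 15% post-randomisation attrition".
- Correlation ρ: Protocol 14.1 discusses the case where the correlation "between baseline and 6-month HbA1c values is at least 0.5", and tabulates 0 to 0.7.

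**Input not in the documents**
- p, the partial correlation of run-in mean glucose with 24-week HbA1c given baseline HbA1c. Assumed range 0 to 0.4.

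**Step 1: reproduce the plan's figures.** Power is from the noncentral t distribution with noncentrality SES × √(64/2) / √(1 − ρ²), on 126 df for the t-test and 125 df for the ANCOVA.
- t-test with 64 per arm: 0.801.
- SES 0.50 at ρ = 0, 0.3, 0.5, 0.7: 0.801, 0.837, 0.900, 0.976 (protocol: 0.80, 0.84, 0.90, 0.98).
- SES 0.44: 0.695, 0.735, 0.814, 0.933 (protocol: 0.70, 0.73, 0.81, 0.93).
- Attrition: 128/0.85 = 150.6, against 150 planned.

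The protocol's table stands. Below, 0.4/0.9 is carried unrounded as 0.444, so the reference power at ρ = 0.5 is 0.821 rather than 0.814.

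**Step 2: add the covariate.** Residual variance becomes SD² × (1 − ρ²) × (1 − p²). The proportional reduction is p², and the equivalent number of evaluable participants is 128/(1 − p²). With ρ = 0.5 and 124 df:

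| p (assumed) | Variance reduction | Extra participants, equivalent | Power, SES 0.50 | Power, SES 0.444 |
|---|---|---|---|---|
| 0 | 0% | 0 | 0.900 | 0.821 |
| 0.1 | 1% | 1.3 | 0.903 | 0.825 |
| 0.2 | 4% | 5.3 | 0.911 | 0.836 |
| 0.3 | 9% | 12.7 | 0.925 | 0.855 |
| 0.4 | 16% | 24.4 | 0.942 | 0.882 |

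**Step 3: confidence interval.** With SD 0.8 and ρ = 0.5, SE = 0.8 × √(0.75 × (1 − p²)) × √(2/64), and the half-width is 1.98 × SE. This gives 0.242 HbA1c points at p = 0, then 0.238, 0.231 and 0.222 at p = 0.2, 0.3 and 0.4.

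**Step 4: what p implies in simple correlations.** Let r12 be the correlation of run-in glucose with screening HbA1c, and r2 its correlation with 24-week HbA1c. Then p = (r2 − ρ × r12) / √((1 − ρ²)(1 − r12²)). With ρ = 0.5 and r12 = 0.7 (assumed):
- r2 = 0.35 (that is, 0.5 × 0.7): p = 0, no gain.
- r2 = 0.40: p = 0.08, reduction 0.7%.
- r2 = 0.50: p = 0.24, reduction 5.9%.
- r2 = 0.60: p = 0.40, reduction 16.3%.

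**Step 5: cost in degrees of freedom.** With the eight centres listed in SAP 4.5, the primary model uses 13 parameters (intercept, arm, HbA1c, seven centre terms, three binary factors), leaving 128 − 13 = 115 residual df. The extra term pays for itself when p² exceeds about 1/115, that is, p above about 0.09.

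**The case against.** The case against is substantial, and most of it limits the size of the point.

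**The gain may be nil.** If the sensor mean tells us about 24-week HbA1c only through what baseline HbA1c already shows, p = 0. A central value such as r2 = 0.5 supposes that two weeks of sensor data predict the outcome as well as HbA1c itself. The calculation also credits the planned model with baseline HbA1c alone; any overlap of run-in glucose with modality, education, bolus calculator use or centre would reduce p. This stands, and is why the range starts at zero.

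**The existing model is sound.** A reader might infer that the primary analysis is wrong, biased or underpowered. The documents do not support that. The ANCOVA is the same in protocol and SAP, it adjusts for the allocation factors, and its power table reproduces.

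**A higher HbA1c correlation does not enlarge the gain.** A reader might expect a bigger benefit at ρ = 0.7. With r12 = 0.7 and r2 = 0.5, p = (0.5 − 0.49)/0.51 = 0.02 and the reduction is 0.04%. For a given p, the power gain is also smaller: at SES 0.444 it goes from 0.937 to at most 0.968 at p = 0.4.

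**The covariate is not guaranteed complete.** A reader might take the run-in rule to mean that every randomised participant has a usable value. For most participants the rule in Protocol 9.4 concerns days worn; the explicit downloaded-data condition covers premature sensor failure. Protocol 14.2.2 adjusts for run-in values only where this can be done, and SAP 3.2.2 lists missed sensor downloads as a deviation category. In a complete-case analysis, a missing run-in value would drop someone with an observed HbA1c and could cancel a small gain. This stands, and it calls for a missing-covariate rule rather than for leaving the variable out.

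**Conclusion.** The omission is real: a required pre-randomisation measure of glycaemia, already used as a covariate elsewhere in the SAP, is missing from the primary model and from the model whose purpose is precision. It is a missed efficiency gain, not an error. For an assumed p of 0 to 0.4, residual variance falls by 0% to 16%. At ρ = 0.5, power goes from 0.821 to between 0.821 and 0.882 at SES 0.444, and from 0.900 to between 0.900 and 0.942 at SES 0.50. Nothing in the documents locates p within that range. The change is worth making because the data are already collected and the cost is close to nothing, not because a particular gain can be promised.

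**What to change.** Before database lock and before any unblinded analysis:

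1. In SAP 5.2.1, and in Protocol 14.2.1 to match, add run-in mean sensor glucose as a continuous covariate in the primary ANCOVA.
2. Add it to the 12-week HbA1c ANCOVA in SAP 5.2.2.
3. Name it in the imputation model in SAP 5.3, so that its inclusion does not depend on whether it predicts missingness.
4. State that the few missing run-in values will be replaced by the simple mean of the observed values, so that no participant with an observed HbA1c is lost.
5. If the primary model must stay as it is, add the variable at least to the precision model in SAP 5.2.3.

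Timing matters because SAP 2.6 says the final analysis is not done blind to treatment group; a covariate added later could look data-driven.

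The cost is one degree of freedom and a change of wording, with no new data, visits or participants. The SAP goes through the review and TSC approval described in Protocol 14.2. If the protocol edit is judged a substantial amendment, Protocol section 20 requires approval from the ethics committee and the sponsor. The fallback in item 5 leaves the protocol text untouched.
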